## **Scientific background**

Invasive mechanical ventilation (IMV), despite saving lives in intensive care unit (ICU), may result in neuromuscular damage and impairment of the respiratory system. This damage can be worsened by immobilization in bed or reduced by using protocols of body positioning.

Body positioning is associated with positive effects on respiratory system among patients requiring invasive mechanical ventilation, mainly when performed outside the bed. For example, the combination of sedestation in a chair and physical activity can improve lung aeration during IMV using endotracheal tube. Accordingly, passive orthostasis with the support of a tilt table has been incorporated into practice in order to allow body positioning of critical care patients outside the bed. When included in daily practice, this strategy, is associated with improvement of the level of consciousness of ICU patients. Moreover, when patients under IMV are placed in passive orthostasis using a tilt table, there is a transient increase in minute volume without a significant change in oxygenation. Nevertheless, the evidence regarding its safety and effectiveness in comparison with other body positioning strategies is still scarce, and the fulfillment of this evidence gap may contribute to improve mobilization outcomes of critically ill patients. Therefore, this study aimed to assess the effects of different mobilization positions on lung aeration of critically ill patients under IMV.

## **Methods**

### **Study design**

The present study was designed to be an open label, randomized, crossover, two-center, clinical trial aimed to assess the impact of different verticalization positions on lung aeration of patients hospitalized in the ICU under invasive mechanical ventilation using endotracheal tube. Patients were enrolled and followed from the medical-surgical ICUs of Ernesto Dornelles (40 beds) and Moinhos de Vento hospitals (17 beds), both tertiary, academic, and private hospitals, in Southern Brazil.

**Sitting position protocol:** Participants were passively placed in bedside sedestation, where they remained for 30 minutes, with back support; their hips and knees were flexed at 90° and feet supported. This position aimed at simulating sitting in a chair.

**Passive orthostasis protocol:** Participants were transferred to a tilt table (0° inclination). Safety straps were placed on the knees, waist and chest to keep participants in the orthostatic position. The tilt table protocol lasted 30 minutes. Initially, participants were placed in a vertical position up to 45° and remained in this position for 3 minutes. Next, they were tilted to 60°, where they remained for 2 minutes. Then verticalization was performed up to 75-85°, where they remained for another 25 minutes.

**Co-interventions:** Endotracheal aspiration was performed 30 minutes before the beginning of both verticalization position protocols. The critical care management of participants, including IMV parameters were left at the discretion of each center assistant team according to local protocols.

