### **Randomization, washout, and bliding**

Subjects were randomized in an 1:1 ratio to one of two sequences of verticalization protocols: sitting position followed by passive orthostasis or passive orthostasis followed by sitting position. Participants were randomized on the same day they were deemed to be suited to participate in the study. Randomization was performed using blocks of different sizes and stratified by center. Allocation concealment was ensured through the use of a centralized webbased randomization plataform (REDCap, Vanderbilt University, Nashville, TN, USA). Researchers had access to intervention sequence only after the participants were registered on the platform. A washout window period (90 to 150 minutes) in which the patient was returned to bed in supine position (end of the first verticalization protocol) was applied between the two verticalization protocols to avoid the carryover effect. Considering the nature of the trial interventions, blinding was not feasible.

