### **Statistical Analysis Plan**

Baseline categorical variables were described as absolute and relative frequencies, while baseline quantitative variables were expressed as mean and standard deviation (SD). Subjects were analyzed according to their randomization group, regardless of treatment they received. Paired Student's T test was used to compare the primary outcome between the two interventions. For secondary outcomes, categorical outcomes were assessed using the McNemar's test, symmetrical continuous outcomes were assessed using the Paired Student 's T test, and asymmetrical continuous outcomes were assessed using the Wilcoxon's signed-rank test. A significance level of 5% was set for all analyses.

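### Does leaving ventilator settings to the care team undermine the paired comparison of the two positions?

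*Combined protocol and SAP*

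**What the plan says.** The Scientific background gives the aim: "this study aimed to assess the effects of different mobilization positions on lung aeration of critically ill patients under IMV". The Study design section describes an "open label, randomized, crossover, two-center, clinical trial", with each position held for 30 minutes. Under Co-interventions one item is standardised: "Endotracheal aspiration was performed 30 minutes before the beginning of both verticalization position protocols". The rest of critical care management, "including IMV parameters were left at the discretion of each center assistant team according to local protocols".

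The section on randomisation, washout and blinding allocates patients 1:1 to the two orders, separates the positions by 90 to 150 minutes in bed, and states: "Considering the nature of the trial interventions, blinding was not feasible". In the Statistical Analysis Plan a paired Student's "T test was used to compare the primary outcome between the two interventions". No covariate, sensitivity analysis or table relating to ventilator settings is mentioned there. The text available has no section on data collection or outcome measurement, so it does not show whether settings were recorded.

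**The concern.** The aim is worded as an effect of position. Ventilator settings can themselves alter lung aeration (a premise of the concern, not a statement in the documents), and the staff who control them can see which position the patient is in. A crossover removes stable differences between patients and centres, and randomised order balances changes that merely come with time. Neither removes a setting change made because the patient is upright on the tilt table rather than sitting.

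The background section offers a possible trigger. On the tilt table "there is a transient increase in minute volume without a significant change in oxygenation", so one ventilatory variable is expected to move in one of the two positions. If staff reacted to it, a significant difference could reflect ventilator management, and a null result could hide a real effect of posture. With no report of settings by position, a reader could not tell which.

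**Working it through.** The plan gives no sample size, SD, effect size or rate of setting changes, so there is no figure to reproduce. What can be checked is the logic and how far it could reach under assumed inputs.

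**Step 1: what the paired difference estimates.** Let p be the share of patients whose settings are changed in a position because of that position, and g the mean effect of such a change on aeration. Then

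E(paired difference) = direct effect of position + (p_tilt × g_tilt − p_sit × g_sit).

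The bracket is a bias only if the target is the direct effect of posture. If the target is position with the ventilator care that goes with it, the bracket belongs to the effect.

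**Step 2: when the bracket is non-zero.** More frequent changes in one position are neither necessary nor sufficient. Simulated mean differences, with no direct position effect and noise SD 1:

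| Changed, tilt vs sitting | Effect per change (SD) | Mean paired difference (SD) |
|---|---|---|
| 20% vs 20% | +1 and +1 | about 0 |
| 30% vs 10% | 0 and 0 | about 0 |
| 30% vs 10% | +1 and +1 | 0.20 |
| 20% vs 20% | +1 and −1 | 0.40 |

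What matters is a net difference in the effect of changes on aeration, through frequency, direction or size.

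**Step 3: effect on the test.** All inputs are assumed: N of 30 or 60, no direct position effect, noise SD of the within-patient difference 1, equal sequences, a common shift per change, two-sided paired t test at 5%, 100,000 simulated trials per scenario. Bias = (p_tilt − p_sit) × shift; for example (0.20 − 0.05) × 1 SD = 0.15 SD.

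| Changed, tilt vs sitting | Shift (SD) | Bias (SD) | Rejection, N=30 | Rejection, N=60 |
|---|---|---|---|---|
| 20% vs 20% | 1 | 0.00 | 5.0% | 5.0% |
| 10% vs 5% | 0.5 | 0.025 | 5.2% | 5.4% |
| 10% vs 5% | 1 | 0.05 | 5.7% | 6.5% |
| 15% vs 5% | 0.5 | 0.05 | 5.7% | 6.6% |
| 15% vs 5% | 1 | 0.10 | 7.8% | 10.8% |
| 20% vs 5% | 0.5 | 0.075 | 6.7% | 8.5% |
| 20% vs 5% | 1 | 0.15 | 11.2% | 18.0% |

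Changes tied only to period (40% of patients, 1 SD) give no bias and a rejection rate of about 4%: with balanced sequences they widen the spread of the differences without moving their mean.

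**Step 4: what a remedy could yield.** Three additions are available.

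- *A table of settings by position.* If no patient among 30 showed a difference, the exact one-sided 95% upper limit would still be 1 − 0.05^(1/30) = 9.5% of patients; among 60 it would be 1 − 0.05^(1/60) = 4.9%.
- *An analysis of patients with unchanged settings.* With 20% and 5% changed independently, 0.80 × 0.95 = 76% remain, about 23 of 30 or 46 of 60. These patients are selected after randomisation, so a disagreement with the full analysis could not be attributed to settings.
- *Adjustment for settings.* Settings changed after positioning are post-randomisation, and possibly a consequence of position, so adjusting for them is not a clean repair.

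None of these replaces the all-patient paired comparison.

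**The case for a change.** The best argument for acting is that the documents never name position under usual ventilator care as the target. The aim reads as position alone, the staff are unblinded, and the background itself expects minute volume to rise on the tilt table. The scenarios above may also understate the problem, since changes in opposite directions at equal frequency give a bias of 0.40 SD. A few recorded fields and one table would cost little.

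The conditional logic stands, and so does the point that the estimand could have been named more exactly. The rest carries less weight:

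- The discretion over settings is openly stated in the same section as the design, and an aim framed around patients under mechanical ventilation is compatible with comparing positions under usual care.
- The documented rise in minute volume is transient and comes without a significant change in oxygenation, which is weak ground for expecting staff to act. A change in ventilation on standing may also be part of how posture works.
- Bias needs a change made because of the position, within a 30-minute exposure, that alters aeration by the time of the reading. No step in that chain is documented.
- Whether settings were recorded cannot be judged from the available text, so an absence of recording is not established. The plan is written in the past tense, so new prospective recording may no longer be possible.

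**Conclusion.** No change to the plan follows. Leaving ventilation to the treating team is a fair trade-off: the comparison keeps clinical decisions where they were and estimates the effect of position under usual ventilator management, for which the paired test is not distorted by setting changes in any scenario above. It would depart from a position-only effect only if setting changes made because of position had a net different effect on aeration. The documents do not show that this happened, and its size is unknown. In the illustrations with a common direction of shift, the false-positive rate for a position-only claim runs from the nominal 5.0% to 11.2% (30 patients) or 18.0% (60 patients), and every input behind those figures is assumed.

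An analyst can deal with this sensibly in the report, by describing the result as position under usual ventilator management and showing charted settings by position where they exist. That affects description only; the primary analysis and its result stay the same. This conclusion rests on reading the aim as compatible with usual ventilator care, and on the absence of any documented position-linked change. It takes no view on how the ventilator should be managed.

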### **Randomization, washout, and bliding**

Subjects were randomized in an 1:1 ratio to one of two sequences of verticalization protocols: sitting position followed by passive orthostasis or passive orthostasis followed by sitting position. Participants were randomized on the same day they were deemed to be suited to participate in the study. Randomization was performed using blocks of different sizes and stratified by center. Allocation concealment was ensured through the use of a centralized webbased randomization plataform (REDCap, Vanderbilt University, Nashville, TN, USA). Researchers had access to intervention sequence only after the participants were registered on the platform. A washout window period (90 to 150 minutes) in which the patient was returned to bed in supine position (end of the first verticalization protocol) was applied between the two verticalization protocols to avoid the carryover effect. Considering the nature of the trial interventions, blinding was not feasible.

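### The primary paired t test ignores the randomised sequence and the stratifying centre, so any order effect would stay in the error term and cost precision

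*Combined protocol and SAP*

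**What the plan says.** The trial is described under Study design as an "open label, randomized, crossover, two-center, clinical trial". Under the randomisation heading, "Subjects were randomized in an 1:1 ratio to one of two sequences of verticalization protocols", and "Randomization was performed using blocks of different sizes and stratified by center". The two periods are separated by a rest in bed: "A washout window period (90 to 150 minutes", introduced to avoid carryover.

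For the primary outcome, the Statistical Analysis Plan says that a paired Student's "T test was used to compare the primary outcome between the two interventions". It names no term for sequence, period or centre, and no supporting model that contains them. The secondary outcomes are handled in the same way, with McNemar's test, the paired t test or the signed-rank test. "A significance level of 5% was set for all analyses"; sidedness is not stated. The sentence "Subjects were analyzed according to their randomization group, regardless of treatment they received" fixes how patients are counted, but it does not put sequence into the analysis.

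**The concern.** Blocking the sequences within centre lets a change between the first and second protocol cancel, or nearly cancel, from the estimated position effect. The paired t test does not carry that benefit into the standard error. In one sequence the change adds to the within-patient difference and in the other it subtracts, and the test treats this systematic spread as noise. Sequence and centre are known for every patient, so the loss is avoidable.

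What is at stake is precision and power for the main comparison. The washout is aimed at carryover and does not remove a period effect. The two periods fall at different times in a critically ill patient's course, while care, "including IMV parameters were left at the discretion of each center assistant team according to local protocols", may differ between the hospitals.

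**Working it through.** **Inputs from the documents.** Two sequences at 1:1, blocks of varying size, two centres, paired t test, 5% level. There is no stated sample size, power, effect or SD, so there is no figure of the plan's own to reproduce.

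**Assumptions.** N = 30; two-sided 5%; centre split 70:30, from the bed counts under Study design (40/(40 + 17) = 0.70); SD of the within-patient difference, apart from order effects, = 1; true position effect 0.53 SD, which gives about 80% power; blocks of 2, 4 and 6. Order effects are in units of that SD and are given as larger centre/smaller centre.

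**Model.** Let D be orthostasis minus sitting for one patient:

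D = τ + s·π_c + e, with SD(e) = 1,

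where s = +1 if sitting comes first and -1 otherwise, and π_c is the period-2 minus period-1 change in centre c. A centre's average aeration level enters both periods and drops out of D.

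**Step 1: mean.** With sequences balanced within centre, s·π_c averages to zero, so mean(D) estimates τ without bias. If n1 and n2 patients are analysed in the two sequences, the bias from a common order effect π is π(n1 - n2)/n. For π = 0.25 and an imbalance of 2 in 30, this is 0.25 × 2/30 = 0.017 SD.

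**Step 2: variance.** Write m for the patient-weighted mean of π_c². The paired t test estimates a variance of about 1 + m·n/(n - 1). The full model (sequence, centre, product) leaves 1. The interval width ratio is therefore about √(1 + m·30/29) × t(29)/t(26), with t(29) = 2.045 and t(26) = 2.056.

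| Order effects | m | Width ratio, paired/full |
|---|---|---|
| 0.2/0 | 0.7 × 0.04 = 0.028 | 1.01 |
| 0.5/0.5 | 0.25 | 1.12 |
| 0/1 | 0.3 | 1.14 |
| 1/0 | 0.7 | 1.31 |

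**Step 3: what a sequence term alone recovers.** It leaves 1 + Var(π_c between centres). For a common order effect that variance is 0, so nothing remains to recover. For a gap of 0.5 SD it is 0.7 × 0.3 × 0.25 = 0.0525, and the SE is about 2.6% too large. For a gap of 1 SD it is 0.21, and √1.21 = 1.10, so 10% too large.

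**Step 4: simulation**, about 4,000 trials per setting. Entries are paired t / sequence only / full model; single entries are for the paired t test.

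| Order effects | 95% CI half-width | Power |
|---|---|---|
| 0/0 | not tabulated | 79.4% / 79.3% / 79.0% |
| 0.5/0.5 | 0.415 / 0.371 / 0.373 | 73% paired, about 80% full |
| 0.75/0.25 | 0.442 / 0.382 / 0.373 | 67% / 78% / 80% |
| 0.25/0.75 | 0.409 | 73% |
| 0.5/-0.5 | 0.415 / 0.410 / 0.372 | 72% / 72% / 79% |
| 1/0 | 0.487 / 0.412 / 0.373 | 58% / 72% / 79% |
| 0/1 | 0.423 | 72% |

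For 0.5/0.5 the simulated width ratio is 0.415/0.373 = 1.11, close to the 1.12 of Step 2. The paired test's actual type I error is 1.2% for 1/0 and about 3% for 0/1.

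**Step 5: sensitivity to centre split and N.** With equal centres and N = 40, the paired/full width ratio is 1.02 for 0.2/0.2, 1.12 for 0.5/0.5, 1.12 for 0.5/-0.5 and 1.23 for 1/0.

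**The case against.** The strongest reply is that nothing in the documents shows an order effect, and without one the paired t test loses nothing. That stands: every loss above is conditional.

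A reader might take the reference to local protocols as evidence that order effects differ between the hospitals. It describes background care. It does not say that care changes between a patient's two periods, still less in opposite directions by centre. Airway suctioning is timed identically before each protocol, and patients lie supine between them. These features do not exclude a period effect, but they make centre-specific shifts of 0.5 to 1 SD speculative.

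A reader might also infer that leaving out the stratification factor is itself the fault. The calculations do not support that. Sequence usually does most of the work: for 0.75/0.25 it raises power from 67% to 78%, and the centre terms add 2 points. For 0.2/0 the sequence-only and full models have practically the same half-width (0.371 and 0.372).

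The largest figure also depends on where the effect lies. A 1 SD shift costs 21 points of power in the larger centre (79% to 58%) but only about 7 in the smaller (79% to 72%).

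Finally, the plan is written in the past tense. If outcome data have been seen, replacing the primary test would be a post hoc change. That limits how the remedy can be labelled; it does not remove the reason for it.

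**Conclusion.** The point holds as a conditional loss of precision. The analysis omits the sequence and centre by which patients were randomised, so any order effect would remain in the error variance. Under the assumptions above, the paired interval is about 1% too wide for small order effects (0.2/0), 11% for 0.5 SD in both centres, and 14% to 31% for 1 SD confined to the smaller or the larger centre. A sequence term recovers essentially all of the loss when the order effect is common to both centres. The sequence-by-centre term matters only when the centres differ substantially. A position effect that differs by centre would also add to the error, but it is not sized here.

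A reader might infer a biased primary result or an excess of false positives. Neither follows. With balanced sequences the error is conservative, and a small bias arises only if the analysed sequences become unequal. N, SD, sidedness, centre split, block sizes and order effects are all assumed. The change is worth making because it is nearly free; the planned test is not invalid.

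**What to change.** For the primary outcome and the symmetrical continuous secondary outcomes, replace the paired t test with a linear model on each patient's difference (orthostasis minus sitting). Include sequence coded +1/-1, centre mean-centred, and their product. The intercept is then the position effect; report it with its 95% CI and test it at 5%. An equivalent choice is a mixed model with position, period, centre, period by centre and position by centre, centre mean-centred, and a random patient effect.

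The coding must be written into the SAP. With 0/1 sequence coding the intercept is the position difference in one sequence only. In the 1/0 setting it would centre on about 0.53 - 0.70 = -0.17 (simulated -0.18) instead of 0.53, with a type I error of 76%.

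For asymmetrical continuous outcomes, compare period differences between sequences with a centre-stratified rank-sum (van Elteren) test. This change does not cover the outcomes assigned to McNemar's test.

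Keep the paired t test as a sensitivity analysis. If outcome data have already been seen, leave the planned test as primary and report the adjusted model as a labelled supporting analysis.

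The cost is SAP wording, a few lines of code and up to three degrees of freedom: about 1 point of power or less at 20 to 30 patients if there is no order effect. No new data or patients are needed.

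### Should the plan have masked the outcome reader and the analyst, instead of calling blinding infeasible for everyone?

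*Combined protocol and SAP*

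**What the plan says.** Under Study design, the document states that "The present study was designed to be an open label, randomized, crossover, two-center, clinical trial". The two conditions described there are unmistakable to anyone present. For sitting, "Participants were passively placed in bedside sedestation"; for passive orthostasis on the tilt table, "Safety straps were placed on the knees, waist and chest to keep participants in the orthostatic position".

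The section on randomization, washout and blinding says "Subjects were randomized in an 1:1 ratio to one of two sequences of verticalization protocols", describes concealment through a central web platform, and closes with the only statement on masking: "Considering the nature of the trial interventions, blinding was not feasible". It does not distinguish patients, clinical staff, outcome readers and the analyst.

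The Statistical Analysis Plan section says nothing about coded labels or a masked analyst. It does fix two things that matter here: "Subjects were analyzed according to their randomization group, regardless of treatment they received", and for the primary outcome a paired Student's "T test was used to compare the primary outcome between the two interventions". For secondary continuous outcomes the test depends on the shape of the distribution: symmetrical ones get the paired t test, and "asymmetrical continuous outcomes were assessed using the" Wilcoxon signed-rank test.

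**The concern.** A single reason is given for every role, and it does not reach every role. Posture cannot be hidden from the patient's nurse or from someone holding a probe at the bedside. It might be hidden from a person who scores a saved recording later under a code number, and it can be hidden from an analyst who receives the two positions as X and Y. An open-label trial can have either.

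If a reader who knew the position scored one posture more favourably, that shift would enter the within-patient difference directly. The features of this design that usually reassure would not remove it. Randomised order balances a shift tied to period, not one tied to position. Pairing removes differences between patients, not a bias within the pair. Allocation concealment protects the assignment, and the document says researchers could see the sequence once a participant was registered.

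The analyst has some latitude too: how a secondary outcome is judged symmetrical or not, and what happens to patients who lack one of the two measurements, whom a paired test drops.

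**Working it through.** **Step 1: does the stated reason hold, role by role?**

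| Role | Does visible posture rule out masking? | What the documents show |
|---|---|---|
| Patient | Yes, if aware | Study design describes both postures |
| Treating staff, bedside operator | Yes | Same |
| Reader of stored recordings away from the bedside | Not by itself | No instrument, recording, reader or scoring method is described |
| Analyst | No | Primary test fixed; no mention of coding |

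**Step 2: does the reader row apply to this trial?** The text names lung aeration as the outcome domain and goes no further. There are three possibilities.

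- Scored live at the bedside: the plan's sentence is right for the reader as well.
- Measured automatically: there is no human judgement to mask.
- Scored by a person from stored recordings: masking could help, provided that the recording does not reveal posture or time and that the reader was not also at the bedside.

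The concern survives only in the third case, and the documents do not say that it occurred.

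**Step 3: how large could a reading bias be?** The documents give neither N nor a shift, so both are assumed. With no true effect and an average shift of d standard deviations of the within-patient difference, the paired t statistic follows a noncentral t distribution with N − 1 degrees of freedom and noncentrality d√N. I take the 5% level as two-sided, which the plan does not state. For example, with d = 0.2 and N = 20 the noncentrality is 0.2 × √20 = 0.894; the critical value is 2.093 and the rejection probability is 13.60%.

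| Assumed d | N = 20 | N = 30 |
|---|---|---|
| 0 | 5.00% | 5.00% |
| 0.05 | 5.52% | 5.81% |
| 0.1 | 7.09% | 8.27% |
| 0.2 | 13.60% | 18.52% |

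In simulation, a shift of the same sizes tied to period left the rate at 4.5% to 5.1%, which confirms that only a position-tied shift matters. The arithmetic is correct, but it shows only that a biased input gives a biased test. It says nothing about whether d differs from zero here. Nor does it show what coding would achieve. Saying that half-effective masking lowers 13.60% to 7.09% merely moves from the d = 0.2 row to the d = 0.1 row.

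**Step 4: what would masking the analyst change?** Swapping the labels reverses the sign of every within-patient difference.

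- Paired t: the statistic changes sign, so the two-sided p-value is unchanged.
- Wilcoxon signed-rank: the positive and negative rank sums exchange, so the two-sided p-value is unchanged.
- McNemar: the two discordant counts exchange, so the two-sided p-value is unchanged.

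An analyst working with X and Y labels could therefore still run both continuous tests and keep the smaller p-value. In simulation that practice raised the error for a single secondary outcome from 5% to about 5.6% to 6.6%. What prevents it is a rule for choosing the test, not masking. The handling of patients without both measurements is likewise a missing-data question.

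**The case for a change.** The best case for acting is that the remedy is cheap. One sentence giving the blinding status of each role would be more accurate than a blanket statement, whichever measurement method was used. Where recordings exist, coding the files costs little and a position-tied reading bias cannot be repaired by the analysis. Labels can also hide the direction of effect while test choices and exclusions are being settled.

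Part of this stands. The sentence is broader than its reason, and a role-by-role account would be clearer. The rest is weaker. The methods are written in the past tense; if the analysis is complete, X and Y labels no longer serve a purpose. A coded re-reading would create a second set of outcome values and raise the question of which set is primary; if the existing reader was also at the bedside, it would need a further reader. Labels also need someone other than the analyst to hold the key, and the documents do not describe the team. Finally, the open-label description is explicit, so the plan does not lead anyone to believe that assessment was masked.

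**Conclusion.** The observation is correct as a matter of wording, but it does not call for a change to the plan. For everyone shown by the documents to be involved at the bedside, the stated reason is sound. For an outcome reader, the risk depends on a fact the available text does not contain, and in two of the three possible measurement settings there is nothing that masking could improve. No size can be attached to it: the false-positive rate stays at 5% if there is no position-tied shift, and the higher figures rest wholly on assumed values of N and d.

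For the analyst, the fixed primary test and analysis as randomised already close the main routes to bias. The remaining latitude in the secondary outcomes is small, at most about 1.6 percentage points for one outcome in the simulated settings (6.6% − 5%), and labels would not remove it.

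This is a gap in reporting detail that the authors can fill sensibly by stating who was unmasked when they report the trial, and listing any unmasked human scoring as a limitation. The conclusion assumes that the text does not elsewhere describe a human reading of stored recordings; if it did, the reader question would deserve a fresh look.
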